## Methods

The camp staff will assign the participating children to one of three different groups (see specifications below). The assignment of children to the various groups will therefore be blinded for the research group.

- SARS CoV-group: The children attending camp Hobro from October 2020 to April 2021 were affected by a COVID19 lockdown of the camps and sent home for 5 weeks with no control of diet and physical activity.
- Control group: The children attending camp Fjordmark from May 2021 to June 2022 will receive the current weight-loss diet (low to moderate protein diet equal to ~15E%/day) for the 10 weeks they attend camp. After leaving the camp, the children and their families will be contacted once every month within the first 6 months and one time halfway between 6 months and 52-weeks follow-up (7 times total). The families will be contacted by phone, face-time, skype as they prefer (see specifications below).
- Protein group (PG): The children attending camp Hobro from May 2021 to March 2022 will be served a higher protein diet equal to ~25E%/day for the 10 weeks they attend camp. After leaving camp they will receive written guidelines and be instructed how to continue a higher consumption of protein-containing foods at home until 52-weeks follow-up. After leaving camp, the children and their families will be contacted once every month within the first 6 months and one time halfway between 6 months and 52-weeks follow-up (7 times total). The families will be contacted by phone, face-time, skype as they prefer (see specifications below).

The trial design is shown in Figure 1, below.

[figure not shown]

Figure 1: Trial design

## The COPE-Study intervention components

### Dietary intervention

The dietary intervention at the multi-component overnight camp uses the official Danish dietary guidelines as basis (33, 34). In all three groups the daily energy intake will be between 1200-1800 kilocalories (kcal) depending on age and gender and a number of foods are limited and restricted for the children during the 10 weeks they attend camp. In the CG and the SARS CoV-group, the protein intake will be ~15E%/day and in the PG the protein intake will be aiming at ~25E%/day. In the PG carbohydrates-rich foods at breakfast and two in between-meals will be replaced by protein containing foods (e.g. dairy products) to make the intervention isocaloric.

The kitchen staff serving meals to the CG will be instructed to continue their usual fixed weight-lost diet plan. Likewise, the kitchen staff serving meals to the SARS CoV-group will be instructed to continue their usual fixed weight-loss diet plan.

The kitchen staff serving meals to the PG will be instructed how to replace some meals by protein containing foods and be responsible for including the predetermined amount of protein foods in the diet plan. After leaving camp the children in the PG will be instructed how to consume protein containing foods as part of their diet until the 52-week follow-up.

### Nutritional education class

All children and their parents will three times total (3-5 weeks before camp; 4-6 weeks into camp; 4-8 weeks after camp) be invited to camp in groups of 8-12 families. All three days they will learn about healthy eating and nutrition.

The CG will be introduced to the official Danish dietary guidelines (33, 34) and be introduced to different foods and recipes to promote healthy eating. The nutritional education class will be an oral presentation performed by the kitchen staff at camp and each session will last 10-15 minutes.

The PG will also be introduced to the Danish dietary guidelines (33, 34) and be introduced to different foods and recipes to promote healthy eating before and after camp. During camp the PG will learn about protein relative to weight loss, satiety and physical activity and furthermore, they will learn how to identify macronutrients, especially protein, in foods. Knowledge of protein and macronutrients will be communicated through story-telling, games and by showing examples of protein containing foods and meals. This session will be held by the primary investigator and last 20-30 minutes.

#### Follow-up intervention

Children and their families attending the PG and the CG will be contacted once every month within the first 6 months' after camp and one time halfway between 6 months and 52-weeks follow-up (7 times total) by the primary investigator.

The conversation with the CG will be about successes and challenges (e.g. concerning healthy eating and physical activity) after camp and the child and their parent/guardian will choose 1-3 issues which they feel is challenging after camp. Those issues will be the main focus at the next follow-up conversation. Likewise, the following follow-up conversations will be based on issues reported as challenging at the last conversation.

The conversation with the PG will primarily focus on protein consumption and before the conversation they will be asked to answer a food frequency questionnaire on protein foods. The primary investigator will motivate the children in the PG to continue eating protein until 52-weeks follow-up.

All children and their families will be contacted by phone, face-time or skype, as they prefer, within a predetermined and known timeframe, and the follow-up conversation will last approximately 10 minutes.

In case of none response the children and their families will receive an SMS reminding them to be in contact with the primary investigator within the week.

#### **Outcome measurements**

The primary outcome measure is BMI-SDS (35) which will be compared between the CG and the PG. BMI will be calculated ( $\text{kg}/\text{m}^2$ ) and weight categories defined using age- and sex-specific BMI-cut-offs from 2007 WHO references (35). Body weight (kg) and fat-free mass/fat-mass will be measured according to standard procedures by using a Bioelectric impedance (InBody model 270). Height (m) will be measured using a fixed wall measuring tape.

Teachers at the multicomponent overnight camps will be instructed how to measure anthropometrics and be responsible for measuring children. Children will be measured three times total; at baseline, 10-weeks and 52-weeks.

One participating parent/guardian will self-report their height and weight at baseline. All measurements are recorded to the nearest 0.1 kg and 0.1 cm.

Additionally, after resting in a chair, all children will have their blood pressure measured at baseline, 10-weeks and 52-weeks. Blood pressure will be measured with the right arm placed at heart level using an automatic non-invasive blood pressure monitor (Omron M3 model). Camp

staff will be instructed how to measure blood pressure correctly and note three measurements at each event from which an average will be calculated.

A blood test will be collected three times total; at baseline, 10 weeks and 52 weeks, from all participating children who voluntarily agrees to a blood test. The blood test will be collected to measure relevant metabolic-, inflammatory- and liver markers.

## **Questionnaires**

Background characteristics will be assessed by a self-developed parent-reported questionnaire with questions concerning parental education, household income, diseases in the family (T2D, hypertension, lipid disorders, ischemic heart disease, thyroid disease), child and parent participation in physical activity (leisure time, sports), ethnicity etc.

Quality of Life will be measured using the Children PedsQL4.0 (36) questionnaire, which is a child-reported questionnaire containing 23 questions.

Children's eating habits will be measured using the Children's Eating Habits Questionnaire-FFQ (CEHQ-FFQ), which is a parent/child-reported questionnaire containing 36 questions (37). Parent and child are encouraged to answer this questionnaire together because it is difficult for the parent/guardian to know exactly which foods their child eat during school and leisure.

Children's eating behaviour will be measured using the Child Eating Behaviour Questionnaire (CEBQ), which is a parent-reported questionnaire containing 35 questions (38).

Children will be asked two questions (see below) from the Eating Disorder examination questionnaire (EDE-Q 6.0) (39) to investigate overeating/loss of control eating episodes and the risk of developing binge eating disorder (BED).

- *No. 13: Over the past 28 days, how many times have you eaten what other people would regard as an unusually large amount of food (in relation to your size and age)?*
- *No. 14: ... On how many of these times did you have a sense of having lost control over your eating (at the time you were eating)?*

Details on the distribution of questionnaires are outlined in Figure 2, below.

Questionnaires will be delivered to the participants using REDcap.

	Aim	- 8 weeks (before camp)	- 4 weeks (before camp)	Baseline (first day)	+10 weeks (end of camp)	+14 weeks	+18 weeks	+ 22 weeks	+ 52 weeks (end of study)
Parent-reported	Background information	X							
	Eating behavior (CEBQ)		X		X			X	X
Parent/child reported	Food habits (CEHQ-FFQ)		X		X			X	X
	Physical activity								X
Child reported	Disturbed eating/BED (EDE-Q)	X	X	X	X	X	X		X
	Quality of life (PedsQL 4.0)		X		X				X

**Figure 2: Distribution of questionnaires**

## Patient health records

We do not need to access patient health records to complete this study.

## Compensation scheme/Insurance

Within the whole study period the participants will be covered by the Act on Complaints and Compensation Access within Health Care (cf. legislation number: 1113 07/11/2011 [www.retsinformation.dk](http://www.retsinformation.dk)). The participants in the trial are covered by the patient compensation scheme.

## Publication of results

Positive, negative and inconclusive results from the **COPE**-study will be submitted for publication in peer-review journals with [name] as first author and presented at scientific conferences from the beginning of year 2023, when some parts of the data are analysed. All analysis and the trial are expected to be finished in 2032. This study is registered and published at clinicaltrials.gov with ID: NCT04522921. All participants will be anonymized in the publication of results.

## Ethics

All parts of the **COPE**-study will be performed in accordance with good clinical practice and conforming to the Declaration of Helsinki. The protocol is approved by the local Committee of Ethics (journal number: 1-10-72-73-20) and the data entering the project will be safeguarded using REDCap database at Aarhus University securing the General Data Protection Regulation. The Data Protection regulation and the Data Protection Act will be complied by all involved parties, researchers and camp staff, when handling trial data. Furthermore, the trial is registered internally at Aarhus University.

Before participation, the nature, purpose and potential risks of the study will be carefully explained to all children and their parents/guardians. All participating children will be invited to follow-up 3 years, 5 years, 7 years and 10 years after the intervention to measure anthropometry

and to answer questionnaires. Also a blood test will be collected from all participating children who voluntarily agrees to a blood test 3 years, 5 years, 7 years and 10 years after the intervention. When the children turn 18 years old, we will provide written and oral information to the adolescents and collect independent written and oral consent from the adolescent. Participants may at any time withdraw from the study without any reason given. All information obtained in the study will be treated as confidential and national authorities will have access to the data if requested.

## **Significance of the project**

The results on weight loss/weight maintenance, biomarkers, QoL, eating habits, eating behaviour and overeating/loss of control eating episodes will provide important information for future weight-loss programmes and report on the effects of increased consumption of protein-containing foods as part of an overall weight-management setting. The access to prospectively follow the cohort and compare the participating children to the other Danish children using a register-based approach will provide invaluable information on the long-term development of disease (e.g. T2D) and various psychosocial factors.

## **Power calculation and statistics**

The power calculation was based on a previous study investigating the effect of a higher protein intake (21E% vs. 32E%) on childhood obesity (28). In this study, 22 and 24 children were allocated to the standard and high protein diet, respectively. Both groups had a reduction in BMI z-score during the 13-week intervention (from  $2.48 \pm 0.06$  BMI-z to  $2.10 \pm 0.10$  BMI-Z in the high protein group, and from  $2.51 \pm 0.05$  BMI-Z to  $2.40 \pm 0.10$  BMI-Z in the standard protein group), with a greater reduction in the high protein group ( $p = 0.03$ ). The number of participants needed to detect a between-group difference of  $-0.27$  SD with a power of 80% and a significance level of 5% was calculated to be  $\sim 55$  children in each group. Preferably, unadjusted mixed effects models will be performed to investigate differences in change between the groups.

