## **Study setup**

The COPE-study is a non-randomized trial and a collaboration with the staff of the multi-component-overnight camps (Julemærkehjem) in Denmark. The multi-component-overnight camps are well-established intensive weight loss camps to which Danish schoolchildren, from 7-14 years of age, are referred to for 10-weeks intervention focusing on a healthy lifestyle, healthy eating, new habits and increased physical activity.

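### An unadjusted model is preferred for a non-randomised, one-camp-per-diet comparison, and no adjusted analysis is prespecified

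*Combined protocol and SAP*

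**What the plan says.** The combined protocol and SAP has one sentence on the analysis model, at the end of Power calculation and statistics: "Preferably, unadjusted mixed effects models will be performed to investigate differences in change between the groups". No section gives a covariate a role in the analysis, and no adjusted sensitivity analysis is described.

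The design is stated plainly. Under Study setup: "The COPE-study is a non-randomized trial". Under Methods: "The camp staff will assign the participating children to one of three different groups". The two groups that matter here are defined by site: "The children attending camp Fjordmark from May 2021 to June 2022 will receive the current weight-loss diet", and "The children attending camp Hobro from May 2021 to March 2022 will be served a higher protein diet". The primary outcome, BMI-SDS, is the one "which will be compared between the CG and the PG" (Outcome measurements).

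Useful covariates are already collected. Age and sex are needed for the "age- and sex-specific BMI-cut-offs from 2007 WHO references". Parental education and household income are in the background questionnaire, which the schedule under Questionnaires places 8 weeks before camp, so they precede the diet. The camp start date is known for every child.

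**The concern.** Under randomisation an unadjusted comparison is unbiased whatever the covariates do. Here that protection is absent: which child receives which diet follows from which camp the child attends. If the two camps' children differ in age mix or family background, and that factor is related to how much BMI-SDS changes, the difference enters the estimated protein effect directly. It could look like a benefit or hide one.

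Modelling change does not settle the matter. It cancels a camp difference that stays constant over time. Standardising BMI for age and sex deals with their relation to the level of BMI. Neither step deals with a factor related to the change itself. If the stated preference is followed, the plan has no prespecified analysis that would show such a problem, and covariates could be chosen after the results are known.

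**Working it through.** **The plan's own figure first.**
- Target difference, from the cited study's means: (2.10 − 2.48) − (2.40 − 2.51) = −0.38 + 0.11 = −0.27, as stated.
- Sample size: the SD is not given. With a two-sided 5% test, 80% power and an assumed SD of 0.50, n = 2 × (0.50 × (1.96 + 0.8416) / 0.27)² = 53.8, so 54 per group by the normal approximation and 55 by the t-test. The stated ~55 is reproduced.
- SD implied by exactly 55: 0.27 / (2.8016 × √(2/55)) = 0.505. I use 0.50.

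**Effect of a bias b on the false-positive rate (no true diet effect).**
- SE = 0.50 × √(2/55) = 0.0953.
- P(reject) = P(|Z + b/SE| > 1.96).
- Take age band as the example, with b = (gap between camps in the share aged 10 or over) × (gap in mean change between age bands). Both gaps are assumptions.

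| Share gap | Response gap | b | False-positive rate |
|---|---|---|---|
| 0.1 | 0.1 | 0.01 | 5.1% |
| 0.2 | 0.2 | 0.04 | 7.0% |
| 0.3 | 0.3 | 0.09 | 15.7% |

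The last row needs a response gap between age bands larger than the whole 0.27 effect that the trial is sized for, so it is an outer bound. A larger sample does not help: at 150 per group SE = 0.50 × √(2/150) = 0.0577, and b = 0.09 gives about 34%.

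**What adjustment does.** With complete data and an unstructured covariance, the group × week-10 term equals a regression of the 0–10 week change on group and covariates, so that regression was simulated (6,000 runs, 55 per group, covariates age, sex, education and income).
- Extreme row: bias 0.090 unadjusted (15.8% rejections), 0.028 with linear age (6.4%), 0.001 with two age bands (5.4%). The form of age therefore has to be fixed in advance.
- No imbalance: 4.7% unadjusted and 4.9% adjusted.
- Power for 0.27, covariates balanced and irrelevant: 80.1% unadjusted, 77.9% adjusted.
- Power for 0.27, 30-point age gap but age irrelevant: 80.5% and 75.4%. Repeat runs put this loss at 5 to 6 points with linear age.
- Week 52, imputation and a start-date term were not simulated.

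**Baseline BMI-SDS.** A separate simulation (4,000 runs, no effect) assumed a camp gap of 0.3 BMI-SDS at baseline and a slope of 0.3.
- If change depends on baseline in the same way in both camps, bias is 0.09 unadjusted, 0.09 with the age, sex, education and income model, and 0.00 with baseline as a covariate.
- If children regress towards their own camp's mean, the three values are 0.00, 0.00 and 0.09 in the opposite direction.

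The documents do not say which case holds, so neither choice is safe by itself.

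**Calendar time.** Methods runs the control group to June 2022 and the protein group to March 2022. Recruitment/consent limits eligible camp starts to March 2022 for both camps. If one window describes starts and the other attendance, the groups may coincide in time; read literally, they do not. Start date or season therefore belongs on the covariate list.

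**The case against.** The strongest case against has four parts.

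- **The wording is permissive.** A reader might infer that the plan rules out adjustment. It does not: the sentence expresses a preference. The gap is that no adjusted model is specified, and this stands.
- **Nothing shows an imbalance.** A reader might infer that the primary result is biased, or that its error rate is 15.7%. The documents support neither. Both camps share the same eligibility criteria. No section says that age, sex, education or income differs by camp or predicts change in BMI-SDS. The Background remark on stronger effects at 10–18 years concerns weight loss in kg under energy restriction, while BMI-SDS is already standardised for age and sex. This objection limits the size of the point, but not the need to plan for it: without randomisation, balance cannot be assumed.
- **Adjustment misses the larger threat.** With one camp per diet, staff, programme and local measurement ("Teachers at the multicomponent overnight camps will be instructed how to measure anthropometrics") coincide with diet, and no child-level covariate separates them. This stands in full. A reader might infer that the adjusted model isolates the protein effect; it would not, and the plan should say so.
- **The exact model is debatable.** Whether to include baseline BMI-SDS is a matter of judgement, as the simulation shows. That argues for fixing the choice openly and reporting the alternative. It does not argue for leaving the model unspecified.

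**Conclusion.** The point holds in a limited form. The plan prefers an unadjusted model for a non-randomised contrast in which diet is fixed by camp, and it specifies no adjusted analysis although suitable variables are collected before the diet starts. That much is certain from the text. Whether any bias results, and how large it is, is unknown. Under the assumed SD of 0.50 and 55 per group, plausible biases of 0.01 to 0.04 BMI-SDS give false-positive rates of 5.1% to 7.0%; 15.7% is an extreme case and should carry little weight. Adjustment would address measured child and family differences only, so the result remains a contrast of camp plus diet. This is a cheap improvement to the plan, not evidence that its result will be wrong.

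**What to change.** Replace the last sentence of Power calculation and statistics with a paragraph that says the following.

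- **Main model:** a linear mixed model of BMI-SDS at baseline, 10 and 52 weeks with group, time and group × time, adjusted for age (form fixed in advance), sex, parental education, household income, and camp start date or season, each with its time interaction. This is the main basis for the control versus protein comparison.
- **Time point:** name whether 10 or 52 weeks carries the conclusion.
- **Beside it:** report the unadjusted model.
- **Sensitivity:** report a version with baseline BMI-SDS as a covariate, because conditioning on baseline in non-equivalent groups can remove or create bias. State that the main model does not adjust for it and that this choice will not change after data are seen.
- **Missing covariates:** state the method, for example multiple imputation.
- **Limitation:** adjustment handles measured child and family differences only. Effects of staff, programme and local measurement cannot be separated from diet.

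No new data are needed. With education and income in three categories each (an assumption, since the categories are not given), the first four covariates use 1 + 1 + 2 + 2 = 6 parameters plus 6 × 2 = 12 time interactions, so 18 fixed effects. A single start-date term adds 1 + 2 = 3. There are two further models to report and missing covariates to handle. The power loss is about 2 to 6 points in the illustration, which leaves out week 52, imputation and the start-date term.

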## **Economic/funding**

The multi-component-overnight camps are financed with the revenue from public sale of Christmas stamps, funding from investors and private companies. The organization behind the camps will provide facilities and staff to help implement and manage the intervention.

The project is funded by an unrestricted grant from Arla Foods Amba on 970,593 Danish kroner (130.000 EUR). Tests, test-instruments, other test-personnel such as bioanalysts, project materials for information, education e.g. and the salary of the primary investigator will be funded by the grant, and payments will continuously be paid as costs arise.

The research team declare no financial interest or affiliation with Arla Foods Amba.

